CLINICAL TRIAL PROTOCOL SYNOPSIS

Name of company:		Tabulated Trial Protocol	
Boehringer Ingelheim			
Name of finished product:			
Name of active ingredient:			
Volasertib (BI 6727)			
Protocol date 16 July 2008	Trial number 1230.4	Planned trial period September 2008 to May 2010	
Title of trial:	An open phase I/IIa trial to investigate the maximum tolerated dose, safety, pharmacokinetics, and efficacy of intravenous BI 6727 as monotherapy or in combination with subcutaneous cytarabine in patients with acute myeloid leukaemia		
Co-ordinating Investigator:	 Telephone:  Fax: 		
Trial sites:	Multicentre		
Clinical phase:	I /IIa		
Objectives:	To investigate the maximum tolerated dose, safety, pharmacokinetics and efficacy of BI 6727 monotherapy and BI 6727 in combination with cytarabine in patients with acute myeloid leukaemia (AML)		
Methodology:	Open label, randomised, controlled, dose escalation		
No. of patients:	 total: 177 enrolled about 143 each treatment: Treatment schedule A (BI 6727 day 1 + 15 in combination with cytarabine): 32 about 21 patients (phase I part) + 44 43 patients (phase IIa part) Treatment schedule B (BI 6727 day 1 + 15 monotherapy): 56 about 21 patients (phase I part) ± including extension cohort up to 15 patients Treatment schedule C (cytarabine control group): 45 43 patients (only phase IIa part)		
Diagnosis and main criteria for inclusion:	Phase I part: Adult patients with relapsed/refractory AML that are not eligible for intensive treatment Phase IIa part: Adult patients with previously untreated acute myeloid leukaemia that are not eligible for intensive treatment		
Test products:	BI 6727 as monotherapy and BI 6727 in combination with cytarabine		

Name of company: Boehringer Ingelheim	Tabulated Trial Protocol	
Name of finished product:		
Name of active ingredient: Volasertib (BI 6727)		
Protocol date 16 July 2008	Trial number 1230.4	Planned trial period September 2008 to May 2010
dose: The starting dose for BI 6727 will be 150 mg. Treatment schedule A: BI 6727 on day 1 + 15 in combination with cytarabine 2 x 20 mg/d on day 1-10 (28-day cycle)	Treatment schedule B: BI 6727 monotherapy on day 1 + 15 (28-day cycle)	
mode of admin. : BI 6727: intravenous infusion (1 hour) Cytarabine: subcutaneous injection		
Reference therapy: Treatment schedule C: cytarabine		
dose: 2 x 20 mg/d on day 1-10 (28-day cycle)		
mode of admin. : subcutaneous injection		
Duration of treatment: Minimum of one 28-day treatment cycle. Patients are eligible for repeated cycles until progression of disease and as long as neither patient nor investigator requests treatment discontinuation.		
Criteria for efficacy, pharmacokinetics and pharmacodynamics: Response, event free survival, relapse free survival, remission duration, overall survival, pharmacokinetics of trial drugs, pharmacodynamic monitoring (biomarker analysis for target inhibition, i.e. FACS analysis for cell cycle arrest, immunocytochemistry).		
Criteria for safety: Maximum tolerated dose, incidence and intensity of adverse events graded according to the common terminology criteria for adverse events (CTCAE, version 3.0), incidence of dose limiting toxicity, laboratory parameters.		
Statistical methods: Exploratory data analyses, conditional power evaluation		

**FLOW CHART FOR TREATMENT SCHEDULE A
BI 6727 + CYTARABINE (PHASE I AND IIA PART OF THE TRIAL)**

Trial Periods	Screen	Treatment							EoT	FU
Cycle *		! 1								
Visit	Screen	1	2	3	4	5	6	7**		
Days	-14 to -1	1 $\forall 1$	5 $\forall 2$	10	15	19 $\forall 2$	23	28 +3		
Informed consent	x									
Demographics	x									
Medical history	x									
Review of in-/exclusion criteria	x	x ^a								
Document ineligibility for intensive treatment	x									
12 lead-ECG (digital, triplicate)	x	x ^b		x ^c				x		
Blood for pharmacogenetics	x ^d									
Physical examination	x						x	x		
ECOG score, weight	x	x					x	x	x	
Height	x									
Vital signs	x	x ^e	x	x	x ^e	x	x	x		
Assignment / Randomisation	x ^f									
Adverse events		x	x	x	x	x	x	x	x	x
Concomitant therapy	x	x	x	x	x	x	x	x		
Administration of BI 6727		x		x						
Administration of cytarabine ^g		x	x	x						
Cytarabine compliance check			x	x	x					
Safety laboratory, incl. urinalysis	x ^h	x ^h	x	x	x ^h	x	x	x ^h		
Serum pregnancy test ⁱ	x						x			
Blood for pharmacokinetics ^k		x	x	x	x			x		
Disease assessment (blood, clinical)	x	x	x	x	x	x	x	x		
Bone marrow aspiration	x ^m	x ⁿ					x ^p			
Eligibility for further cycle							x			
Outcome (remission, progression, death)								x	x	
Other anti-leukaemia therapy									x	
Conclusion of patient participation								x		

EoT end of treatment

FU follow-up

* the visit number follows the cycle number, i.e. visit 2 cycle 1 will read C1_V2 and visit 2 cycle 2 will read C2_V2 and so forth

** can be the same day as visit one of the next cycle. Can be up to 3 days later, but must not be earlier than day 28

- a on day one of the very first cycle only
- b ECGs are performed at time points specified in 5.2.7 and 6.2.2.1. In the first and second cycle ECGs are performed in triplicate at the related PK sampling time points. Furthermore triplicate ECGs are performed before and at the end of every subsequent BI 6727 infusion.
- c ECGs are performed at time points specified in 5.2.7 and 6.2.2.4. In the first and second cycle ECGs are performed in triplicate at the related PK sampling time points. Furthermore triplicate ECGs are performed before and at the end of every subsequent BI 6727 infusion.
- d optional, only after separate informed consent
- e pre-infusion, and at minutes 30 (≤ 5), 60 (≤ 10) and 120 (≤ 10) after start of BI 6727 infusion
- f before the first administration of the trial drug and after informed consent and review of in- and exclusion criteria
- g subcutaneous cytarabine is administered twice daily on day one until ten
- h including coagulation parameters (see section 5.2.5)
- i for women with childbearing potential at screening and after every other cycle
- k sampling at the time points as specified in table 1 in section 10.1.2. In cycle 2 only at -0.05 and 1 hour after dose.
- m within 14 days before first treatment. Cytogenetics and molecular genetics (see 5.3.4). Pharmacodynamic analysis, i.e. FACS and cytospins (see 5.6)
- n only in the first cycle on day 2, i.e. 24 hours after the end of the first BI 6727 administration: Pharmacodynamic analysis (see section 5.6)
- p initial response assessment after the first treatment cycle, this analysis may be performed up to 3 days earlier to allow for a timely continuation of the treatment. Pharmacodynamic analysis (FACS and cytospins, see section 5.6) at the end of the first cycle.
Bone marrow aspiration after repeated cycles according to 5.1.1. Additional bone marrow aspiration as necessary for confirmation of haematologic DLT (see section 5.2.3) or progressive disease.

FLOW CHART FOR TREATMENT SCHEDULE B
BI 6727 MONOTHERAPY (ONLY PHASE I PART OF THE TRIAL)

Trial Periods	Screen	Treatment							EoT	FU ^s
Cycle *		! 1								
Visit	Screen	1	2 ^t	3 ^t	4	5 ^t	6 ^t	7 ^{**}		
Days	-14 to -1	1 $\forall 1$	5 $\forall 2$	10 $\forall 2$	15 $\forall 2$	19 $\forall 2$	23 $\forall 2$	28 +3		
Informed consent	x									
Demographics	x									
Medical history	x									
Review of in-/exclusion criteria	x	x ^a								
Document ineligibility for intensive treatment	x									
12 lead-ECG (digital, triplicate)	x	x ^b		x ^c				x		
Blood for pharmacogenetics	x ^d									
Physical examination ^q	x						x	x		
ECOG score, weight ^q	x	x					x	x	x	
Height	x									
Vital signs ^q	x	x ^e	x	x	x ^e	x	x	x		
Assignment / Randomisation	x ^f									
Adverse events		x	x	x	x	x	x	x	x	x
Concomitant therapy	x	x	x	x	x	x	x	x		
Administration of BI 6727		x		x						
Safety laboratory, incl. urinalysis ^q	x ^h	x ^h	x	x	x ^h	x	x	x ^h		
Serum pregnancy test ⁱ	x							x		
Blood for pharmacokinetics ^k		x	x	x	x			x		
Disease assessment (blood, clinical) ^r	x	x	x	x	x	x	x	x		
Bone marrow aspiration ^r	x ^m		x ⁿ					x ^p		
Eligibility for further cycle							x			
Outcome (remission, progression, death)								x	x	
Other anti-leukaemia therapy									x	
Conclusion of patient participation								x		

EoT end of treatment

FU follow-up

* the visit number follows the cycle number, i.e. visit 2 cycle 1 will read C1_V2 and visit 2 cycle 2 will read C2_V2 and so forth

** can be the same day as visit one of the next cycle. Can be up to 3 days later, but must not be earlier than day 28

- a on day one of the very first cycle only
- b ECGs are performed at time points specified in 5.2.7 and 6.2.2.1. In the first and second cycle ECGs are performed in triplicate at the related PK sampling time points. Furthermore triplicate ECGs are performed before and at the end of every subsequent BI 6727 infusion. After approval of Protocol Revision I, ECG should be performed prior to and at the end of volasertib infusions as single reads using a local ECG machine.
- c ECGs are performed at time points specified in 5.2.7 and 6.2.2.4. In the first and second cycle ECGs are performed in triplicate at the related PK sampling time points. Furthermore triplicate ECGs are performed before and at the end of every subsequent BI 6727 infusion. After approval of Protocol Revision I, ECG should be performed prior to and at the end of volasertib infusions as single reads using a local ECG machine.
- d optional, only after separate informed consent
- e pre-infusion, and at minutes 30 (± 5), 60 (± 10) and 120 (± 10) after start of BI 6727 infusion
- f before the first administration of the trial drug and after informed consent and review of in- and exclusion criteria
- h including coagulation parameters (see section 5.2.5)
- i for women with childbearing potential at screening and after every other cycle
- k sampling at the time points as specified in table 2 in section 10.1.2. In cycle 2 only at -0.05 and 1 hour after dose.
- m within 14 days before first treatment. Cytogenetics and molecular genetics (see 5.3.4). Pharmacodynamic analysis, i.e. FACS and cytospins (see 5.6)
- n only in the first cycle at visit 2, i.e. 5±1 days after the end of the first BI 6727 administration: Pharmacodynamic analysis (see section 5.6)
- p initial response assessment after the first treatment cycle, this analysis may be performed up to 3 days earlier to allow for a timely continuation of the treatment. Pharmacodynamic analysis (FACS and cytospins, see section 5.6) at the end of the first cycle.
Bone marrow aspiration after repeated cycles according to 5.1.1. Additional bone marrow aspiration as necessary for confirmation of haematologic DLT (see section 5.2.3) or progressive disease.
- q After approval of Protocol Revision I, physical examination, vital signs, weight, ECOG score, and safety laboratory incl. urine analysis should be done as medically indicated at discretion of the investigator. The results should be recorded in the source data only; documentation in the eCRF is not required.
- r After approval of Protocol Revision I, disease assessments and bone marrow aspirations only have to be performed per local standard of practice to support the decision on further treatment with volasertib. The results should be recorded in the source data only; documentation in the eCRF is not required.
- s After approval of Protocol Revision I, FU is completed 21 days after discontinuation of study drug.
- t After approval of Protocol Revision I, Visits 2, 3, 5, and 6 are optional.

**FLOW CHART FOR TREATMENT SCHEDULE C
CYTARABINE MONOTHERAPY (ONLY PHASE IIA PART OF THE TRIAL)**

Trial Periods	Screen	Treatment							EoT	FU
Cycle *		! 1								
Visit	Screen	1	2	3	4	5	6	7**		
Days	-14 to -1	1 ∀1	5 ∀2	10 ∀2	15	19 ∀2	23	28 +3		
Informed consent	x									
Demographics	x									
Medical history	x									
Review of in-/exclusion criteria	x	x ^a								
Document ineligibility for intensive treatment	x									
12 lead-ECG	x								x	
Blood for pharmacogenetics	x ^d									
Physical examination	x							x	x	
ECOG score, weight	x	x						x	x	x
Height	x									
Vital signs	x	x	x	x	x	x	x	x		
Assignment / Randomisation	x ^f									
Adverse events		x	x	x	x	x	x	x	x	x
Concomitant therapy	x	x	x	x	x	x	x	x		
Administration of cytarabine ^g		x	x	x						
Cytarabine compliance check			x	x	x					
Safety laboratory, incl. urinalysis	x ^b	x ^h	x	x	x ^b	x	x	x ^b		
Serum pregnancy test ⁱ	x							x		
Blood for pharmacokinetics ^k		x								
Disease assessment (blood, clinical)	x	x	x	x	x	x	x	x		
Bone marrow aspiration	x ^m							x ^p		
Eligibility for further cycle								x		
Outcome (remission, progression, death)									x	x
Other anti-leukaemia therapy										x
Conclusion of patient participation								x		

EoT end of treatment

FU follow-up

* the visit number follows the cycle number, i.e. visit 2 cycle 1 will read C1_V2 and visit 2 cycle 2 will read C2_V2 and so forth

** can be the same day as visit one of the next cycle. Can be up to 3 days later, but must not be earlier than day 28

- a on day one of the very first cycle only
- d optional, only after separate informed consent
- f before the first administration of the trial drug and after informed consent and review of in- and exclusion criteria
- g subcutaneous cytarabine is administered twice daily on day one until ten
- h including coagulation parameters (see [section 5.2.5](#))
- i for women with childbearing potential at screening and after every other cycle
- k sampling at the time points as specified in [table 3 in section 10.1.2](#)
- m within 14 days before first treatment. Cytogenetics and molecular genetics (see [5.3.4](#)). Pharmacodynamic analysis, i.e. FACS and cytospins (see [5.6](#))
- p initial response assessment after the first treatment cycle, this analysis may be performed up to 3 days earlier to allow for a timely continuation of the treatment. Pharmacodynamic analysis (FACS and cytospins, see [section 5.6](#)) at the end of the first cycle.
Bone marrow aspiration after repeated cycles according to [5.1.1](#). Additional bone marrow aspiration as necessary for confirmation of haematologic DLT (see [section 5.2.3](#)) or progressive disease.

ABBREVIATIONS

µL	Mikrolitre
µmol	Mikromol
AE	Adverse Event
ALT	Alanine amino transferase
AML	Acute myeloid leukaemia
APL	Acute promyelocytic leukaemia
aPTT	Activated partial thromboplastin time
Ara-C	Cytarabine
Ara-CTP	Cytosine arabinoside triphosphate
AST	Aspartate amino transferase
AUC	Area under the concentration-time curve
BI	Boehringer Ingelheim
BLQ	Below the limit of quantification
C	Celsius
CA	Competent (Regulatory) Authority
CFR	Code of Federal Regulations
CL	Total clearance
cm	Centimetre
C _{max}	Maximum measured concentration
CML	Clinical Monitor Local
CPK	Creatine phosphokinase
CR	Complete remission
CRA	Clinical Research Associate
CRF/eCRF	Case Report Form / electronic Case Report Form
CRI	Complete remission with incomplete blood count recovery
CRO	Contract research organisation
CTCAE	Common terminology criteria for adverse events
CTMF	Clinical Trial Master File
CTP	Clinical Trial Protocol
CTR	Clinical Trial Report
d	Day
DLT	Dose limiting toxicity
DMPK	Drug Metabolism and Pharmacokinetics
DNA	Deoxyribonucleic acid
DOC	Documentation of Change
EC/IEC	Ethics Committee / Independent Ethics Committee
EC50	Half maximal effective concentration
ECG	Electrocardiogram
ECOG	Eastern Cooperative Oncology Group
EDC	Electronic Data Capture
EFS	Event free survival
EOT	End of treatment
EU	European union
FAB	French-American-British

FACS	Fluorescence activated cell sorting
FDA	Food and Drug Administration
FU	Follow up
GCP	Good Clinical Practice
G-CSF	Granulocyte colony stimulating factor
GLP	Good laboratory practice
GmbH	Gesellschaft mit beschränkter Haftung (german for limited liability company)
gMean	geometric mean
h	Hour
i.v.	intravenous
IB	Investigator's brochure
IC ₅₀	half maximal inhibitory concentration
ICH	International Conference on Harmonisation
IEC	Independent Ethics Committee
INN	International Nonproprietary Name
INR	International normalized ratio
ISF	Investigator Site File
KG	Kommanditgesellschaft
kg	Kilogramm
L	Litre
LD-Ara-C	Low dose Ara-C
MedDRA	Medical dictionary for regulatory activities
mg	Milligramm
min	Minute
mL	Millilitre
MRT	Mean residence time
MTD	Maximum tolerated dose
NC	Not calculated
No.	Number
NOA	Not analyzed
NOP	No peak detectable
NOR	No valid result
NOS	No sample
NSCLC	Non small cell lung cancer
OS	Overall survival
PD	Progressive disease
pH	Potentia hydrogenii
PK	Pharmacokinetic
Plk	Polo like kinase
PR	Partial remission
PT	Prothrombin time
RBC	Red blood cell count
s.c.	Subcutaneous
SAE	Serious Adverse Event
SDV	Source data verification

SOP	Standard Operating Procedure
SPC	Summary of product characteristics
SUSAR	Suspected Unexpected Serious Adverse Reaction
$t_{1/2}$	Terminal half-life
TDMAP	Trial data management and analysis plan
t_{max}	Time from dosing to maximum measured concentration
ULN	Upper level of normal
V_{ss}	Apparent volume of distribution at steady state
V_z	Apparent volume of distribution during the terminal phase
WBC	White blood cell count
WHO	World health organisation

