6.2.3.2 Follow-up visit

Follow-up visits will be performed after the EoT visit in case patients are not eligible for further treatment cycles until death, lost to follow-up or agreement between sponsor and coordinating investigator not to pursue further follow up visits. Follow-up visits should be performed at 12 weeks intervals or earlier if appropriate. Follow-up visits may also be performed by telephone interview in case the patient is unable to visit the investigator. The following will be obtained and / or performed.

- ! ECOG performance score

- ! AEs since last visit in case they occurred during the observational period (6 weeks after the last trial drug administration) or are considered drug-related (see [5.2.1](#) and [8.4.1](#))
- ! Follow-up of AEs in case they were not yet recovered at EoT
- ! Outcome: date death (if applicable), date of progression (in case, the patient experienced PD)
- ! Treatment with any other antileukaemia drug (report date of treatment and drug)

After approval of Protocol Revision I, Follow-up is completed 21 days after discontinuation of study drug.

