7.3.1.2 Assessment of the primary efficacy endpoint and derived variables

The primary endpoint for efficacy is best objective response derived from the data of all cycles. The primary analysis will be done for all patients of the full analysis set (phase II) for all treatment schedules separately. Each patient will be assigned to one of the response categories described in [section 5.1.1.1](#).

Each patient's best response will be used as a primary measure. To describe response over time, the proportions of patients in each response category will be tabulated at specified time intervals.

The number of patients with objective response (best response is CR or CRi) will be summarised. Patients will be followed up for assessment of response and progression until they progress, receive any other anti-leukaemia therapy, die, or until the trial ends. The observed length of follow-up and the number of patients available for analysis at each time point will determine the period of time covered in tables and figures.

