5.2 SECONDARY ENDPOINTS

5.2.1 Event free survival

Event-free survival (EFS) [days] is the shortest duration of the following:-

- dates of assessment indicating 'progressive disease' on RESPONSE page of eCRF – date of randomisation + 1day,
- dates of assessment indicating 'clinical progressive disease' on DISEASS or RESPONSE-page of eCRF – date of randomisation + 1day,
- dates of assessment indicating 'progressive disease' on PAT_STATUS of eCRF – date of randomisation +1 day (for patients who have not been censored before, see below)
- death date – date of randomisation +1day.

Date of assessment refers here to the progt as given in the eCRF. If progt is missing then the corresponding examdt will be taken instead if available. Progression events are only taken into account if the corresponding date is before the start date of a new anti-leukemia therapy (see below for censored patients).

Patients not being assessed 'progressive disease', clinical progressive disease' or death during the trial will be censored as described below. These patients must be reviewed on a case by case basis by the trial statistician (TSTAT) and trial clinical monitor (TCM).

Right censoring rule for event-free survival (EFS):

Patients getting a new additional other anti-leukemia therapy recorded at the eCRF (follow-up) but not being assessed 'progressive disease', clinical progressive disease' or death before the new anti-leukemia therapy was started will be censored at the date of last disease assessment before the new anti-leukemia therapy was started (excluding follow-up).

Event-free survival censored [in days] is the time from randomisation to the date of last visit (Date of last visit (including follow-up) – date of randomisation + 1 day) for all other patients not being assessed 'progressive disease', clinical progressive disease' or death at the time of data base lock. Date of last visit does not include visit dates from follow-up where 'lost to follow-up' = yes.

EFS will be reported in days.

Patients without any response assessment (best overall response = no assessment) and without death will be censored with an EFS of 0. Otherwise the death date will be used.

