5.2.3 Relapse-free survival, remission duration and time to remission

Relapse-free survival / Remission duration is defined only for patients with a best overall response of CR or CRi.

Relapse-free survival [in days] = (date of first recurrence of disease or death after entering the trial – date of first occurrence of CR or CRi after entering the trial + 1 day) for patients with a recurrence (this value should be positive).

Relapse-free survival (censored) [in days] = (date of last trial visit (or follow-up) - date of first occurrence of CR or CRi after entering the trial + 1 day) for patients who did not yet experience recurrence of disease or death at the time of analysis.

Remission duration is defined analogously with the exception of censoring patients that die before recurrence.

Time to remission [in days] = (date of first occurrence of CR or CRi after entering the trial – date of randomisation + 1 day) for patients with an objective response (this value should be positive).

Date of first recurrence of disease is given by the first date of being assessed as either 'progressive disease', 'clinical progressive disease' or death after the first occurrence of CR or CRi after entering the trial. If a patient has either no date of being assessed as either 'progressive disease', 'clinical progressive disease' or death or no occurrence of CR or CRi after entering the trial this date is missing and will also not be imputed.

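### EFS, relapse-free survival and remission duration are censored at the last follow-up contact, but follow-up schedules no leukaemia assessment, so progression that goes unreported counts as event-free time

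*Protocol*

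**What the plan says.** **Assessment schedule.** The flow charts for schedules A, B and C mark the row "Disease assessment (blood, clinical" eight times, at screening and visits 1 to 7, with no mark under EoT or FU. Protocol 6.2.3.1 requires an assessment at end of treatment only if none was done in the preceding four weeks. Protocol 6.2.3.2 sets follow-up at 12-week intervals, or earlier if appropriate. It collects ECOG score, adverse events, date of death, date of progression where it has occurred, and other anti-leukaemia treatment. No blood, marrow or clinical leukaemia assessment is listed, and "Follow-up visits may also be performed by telephone interview in case the patient is unable to visit the investigator".

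**Stated intent.** Protocol 7.3.1.2 is broader: "Patients will be followed up for assessment of response and progression until they progress", start another anti-leukaemia therapy, die, or the trial ends. It names no test and no interval.

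**EFS censoring (SAP 5.2.1).** There are three rules:
- The default is "Event-free survival censored [in days] is the time from randomisation to the date of last visit (Date of last visit (including follow-up").
- Patients who start new anti-leukaemia therapy without an earlier event "will be censored at the date of last disease assessment before the new anti-leukemia therapy was started (excluding follow-up").
- Patients with no response assessment and no death are censored at 0.

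**Relapse-free survival and remission duration (SAP 5.2.3).** Censored relapse-free survival runs from first CR or CRi to the last trial visit or follow-up: "date of last trial visit (or follow-up) - date of first occurrence of CR or CRi after entering the trial". Remission duration is analogous, except that deaths before recurrence are censored. Neither has a new-therapy rule.

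**The concern.** A censoring date should be the last date on which the patient was known to be free of the event. In this trial, progression and relapse are defined by blasts in blood or marrow, extramedullary disease or clinical deterioration. A 12-weekly contact that may be a telephone call can report a progression already found elsewhere, but a contact with nothing to report is not a negative assessment. Under the default rule it is treated as one.

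The SAP does not apply one principle throughout. Two of its three EFS rules give no credit for unassessed time; the default rule does. Relapse-free survival and remission duration lack the new-therapy rule altogether, so a responder given another drug after end of treatment stays relapse-free up to the last contact.

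What is at stake is the length of the three time-to-event summaries and, if the arms differ in how often patients stop without progression, the exploratory EFS log-rank test in SAP 7.5.

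**Working it through.** **The plan's own figure.** The documents give no event count, hazard ratio or power for these endpoints. The only sized comparison is response: 86 patients, 78.3% power. That reproduces at 43 per arm (77.6% to 79.1% by variance formula) and has no bearing here.

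**Step 1: who is exposed.** For EFS, a patient must stop without progression, start no new therapy, and then progress without a report. For relapse-free survival and remission duration, the middle condition drops out.

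**Step 2: how much can happen in one interval.** Take an exponential time to progression with median m days (assumed). The probability of progressing within 12 weeks (84 days) is 1 − 2^(−84/m).

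| Median m (days) | Calculation | Probability |
|---|---|---|
| 90 | 1 − 2^(−0.933) | 0.476 |
| 120 | 1 − 2^(−0.700) | 0.384 |
| 180 | 1 − 2^(−0.467) | 0.276 |

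So about 28% to 48% of such patients would progress inside a single unassessed interval.

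**Step 3: effect on a null EFS comparison.** The simulation used these inputs.
- From the documents: 28-day assessments on treatment and 12-weekly contacts afterwards.
- Assumed: equal progression hazard in both arms, exponential times, median death 4 months after progression, cut-off at 8 to 24 months, no new therapy, and median time to stopping without progression of 6 months in one arm and 12 in the other.
- Size: 60,000 patients per arm.

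A hazard ratio below 1 favours the arm that stops more. The last column is a reference only, in which follow-up carries an assessment every 12 weeks.

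| Median time to progression | Follow-up progression reported | HR, planned rule | HR, reference |
|---|---|---|---|
| 6 months | none | 0.91 | 0.99 |
| 6 months | half | 0.95 | 0.99 |
| 3 months | none | 0.90 | 0.97 |
| 3 months | half | 0.93 | 0.97 |

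With all follow-up progression reported, smaller runs (6,000 per arm) gave 0.97 to 0.98 under the planned rule, and runs under other assumed settings gave 0.99 to 1.02.

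Swapping the stopping rates reverses the tilt. At a 6-month median the planned rule then gives 1.09 (none reported) and 1.06 (half reported).

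**Step 4: effect on the medians.** At a 6-month median with no reporting, median EFS was 8.3 and 7.4 months under the planned rule, against 6.7 and 6.5 in the reference. The lengthening is therefore present in both arms. At a 3-month median all four values were 3.7 months, so the median need not move.

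**Step 5: against sampling error.** With d events split evenly, the standard error of log HR is about 2/√d. For an assumed 50 to 80 events that is 0.28 to 0.22. Since ln 0.91 = −0.094, the shift is 0.094/0.28 = 0.3 to 0.094/0.22 = 0.4 standard errors.

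**Step 6: candidate repairs under the same null.** Censoring event-free patients at the last assessment while still counting follow-up progressions and deaths gave hazard ratios up to 1.13. It keeps follow-up for patients with events and discards it for those without. Ignoring all follow-up for every patient who leaves treatment without progression gave 0.97 to 1.02.

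**The case against.** The strongest reply is that follow-up is not blind to progression, and the documents bear this out:
- The flow charts collect outcome at EoT and FU, and Protocol 6.2.3.2 asks for a progression date.
- SAP 5.2.1 counts progression on the patient-status page as an EFS event.
- Protocol 5.1.1 calls for marrow examination when progression or relapse is suspected.
- Protocol 5.1.1.1 asks that objective progression be documented even after treatment stops, and Protocol 7.4 wants follow-up for progression to limit missing data.
- SAP 5.2.1 has event-free EFS patients reviewed case by case, and SAP 7.5 lists those without an assessment in the 42 days before discontinuation.

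All of this stands. It means that ascertainment in follow-up is unscheduled, not absent. It does not close the gap: examination on suspicion needs someone to suspect, the case review has no stated criterion or consequence, and the 42-day check looks back from treatment discontinuation only.

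A reader might also infer that EFS is tilted toward the combination, as the more myelosuppressive arm. The documents do not support that. They give no stopping rates by arm. Protocol 4.1.4 provides for re-evaluation of blood counts for up to three weeks and for continuation after recovery from a DLT, so more toxicity need not mean more stopping without progression.

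On weight, the objection is right that these endpoints are secondary and exploratory. Remission duration has no formal arm comparison, and the relapse-free curves carry no p-values (SAP 7.5).

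**Conclusion.** The point holds in a limited form. The default censoring date for all three endpoints is a contact at which no leukaemia assessment is scheduled, so progression or relapse that is not reported is counted as event-free time. This can lengthen EFS, relapse-free survival and remission duration in either arm.

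A between-arm effect needs a further condition, that the arms differ in stopping without progression. The null EFS hazard ratio then moves to about 0.90 to 0.95 in favour of the arm that stops more if half or less of follow-up progression is reported, and stays close to 1 if all is reported. Stopping rates, progression times and reporting shares are assumptions. Relapse-free survival and remission duration were not simulated.

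The shift is small beside sampling error with 43 patients per arm. Objective response is untouched, because SAP 5.1.2 counts best response only to end of treatment. The case for acting rests on the SAP's uneven censoring rules and on a cheap repair.

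**What to change.** 1. Keep the planned censoring rule as the main analysis.
2. In SAP 5.2.1, 5.2.3 and 7.5, add a sensitivity analysis of EFS and relapse-free survival. Censor every patient who leaves treatment without progression at the last documented on-study disease assessment, and do not count events after that date. Use of follow-up then does not depend on outcome.
3. Apply the existing EFS new-therapy rule to relapse-free survival and remission duration.
4. Report the main and sensitivity results side by side.

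Do not make last-assessment censoring the main rule while follow-up progressions and deaths still count as events; that biases EFS downward (step 6 of the working).

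Cost: SAP wording and two extra runs. The assessment dates are already on the eCRF pages that SAP 5.2.1 reads, so no new test or data item is needed. The sensitivity run has fewer events, leaves out some deaths although EFS includes death from any cause, and may itself censor informatively. It therefore supports the main analysis and does not replace it.
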